8.2 Handling of Missing Data

Should a determination of treatment period (on treatment, pre-treatment, follow-up) be required for adverse events or concomitant medication but the corresponding date is missing, or is a partial date, the event/medication will be considered on treatment unless the portions of the date that are available indicate this is not possible.

If a subject fails to complete their eDiary for a week or more, the WI-NRS endpoints, including the primary endpoint, may be missing. In this case, the WI-NRS change from baseline value will be imputed. The approach uses the subject's last week with data. From that point forward their trajectory will be imputed based upon the trajectory of their treatment group.

The imputation approach first determines the average change for each week for each treatment group. The difference in the weekly measures between weeks n-1 and n will be considered the change for Week n. Any missing changes will be imputed to produce and them combined with the prior known value to produce a change from baseline result. For

example, a placebo subject with known results at Week 4 but missing at Week 6 will have their Week 6 WI-NRS change from baseline imputed as $\Delta_4 + \Delta_{P(4-6)}$, where Δ_4 is the observed change from baseline result for the subject up to Week 4 and $\Delta_{P(4-6)}$ is the average placebo change from Week 4 to 6 (i.e. the average placebo decrease from Week 4 to 6).

For the responder endpoints, the same imputation will be performed and the responder status determined based upon the change from baseline and the subject's disposition and rescue medication status (See [Section 8.8](#)).

As a sensitivity analysis, a similar approach will be used where the imputation step uses multiple imputation methodology.

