1.6 Decision Rule and Sample Size

The significance level for this study is 5% (one-sided). If the one-sided p-value is less than 5% then the null hypothesis of no treatment effect is rejected. If the one-sided p-value is additionally less than 2.5%, then the serlopitant-based regimen will have met the generally accepted level of evidence required to demonstrate efficacy.

The target sample size of 200 randomized and dosed subjects (100 per group) has been determined based upon a 1:1 allocation of subjects to treatment groups and a 5% one-sided alpha level. A sample size of 200 subjects results in at least 90% power assuming a placebo 4-point responder rate of ███% and serlopitant 4-point responder rate of ███% at Week 10.

The sample size calculations have been performed in PASS 13 (“PASS 13 Power Analysis and Sample Size Software” 2014) and used a Chi-Squared test. The primary analysis will control for the stratification factors. It is expected that this unstratified power estimate will under-estimate the true power as it does not take the variance reduction resulting from stratification into account ([Matts and Lachin 1988](#)).

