2.5.1 Primary Analysis

The difference in the primary efficacy outcome measure (WI-NRS 4-point responder rate at Week 10) between treatment groups will be summarized by treatment group. The difference in responder rates between treatment arms will be tested using a Cochran-Mantel-Haenszel (CMH) test controlling for the ‘as randomized’ stratification factors. Conceptually, the hypotheses being tested are:

$$H_0: \pi_p \geq \pi_s \qquad H_a: \pi_p < \pi_s$$

where π_p is the placebo responder rate at Week 10 and π_s is the similar measure for serlopitant.

The primary endpoint will utilize the analysis windows outlined in [Section 2.4](#), the intercurrent rules outlined in [Section 2.6](#), and the missing data rules outlined in [Section 2.7](#).

2.5.2 *Secondary Analyses*

Secondary endpoints will be summarized with descriptive statistics by time point and treatment. These summary measures will include baseline, result at the time point, and change from baseline as is appropriate for the endpoint. Missing data imputation will be limited to the WI-NRS endpoint.

The differences between treatment groups for the WI-NRS 4-point at Weeks 2, 4, 6, and 8, and 3-point responder rates at Weeks 2, 4, 6, 8, and 10 will be tested using the CMH test identical to the one used for the primary endpoint.

The change from baseline to Weeks 2, 4, 6, 8, and 10 for the WI-NRS will be tested using an analysis of variance (ANOVA) model with treatment group and stratification factor as fixed effects. A separate model/test will be performed at each time-point. [REDACTED]

CCI

[REDACTED]

The change in WI-VAS to Weeks 2, 4, 6, and 10 will be tested using a similar ANOVA model.

2.6 **Intercurrent Event**

Intercurrent events include withdrawal from the study due to lack of efficacy or rescue therapy use for treatment of worsening pruritus. Rescue therapy will be identified by the site who indicate if medications were taken to treat worsening of pruritus.

Subjects who withdraw from the study early following stopping treatment due to an intercurrent event will have WI-NRS datapoints following the events set to the larger of baseline and the last WI-NRS value prior to the event. For rescue therapy this value will be imputed from the start of rescue therapy to 4 weeks after the end of this therapy. This approach will result in subjects being defined as non-responders following the intercurrent event.

[figure not shown]

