The missing data rules outlined in [Section 2.7](#) will not be used for the results following an intercurrent event.

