2.7 Handling of Missing Data

Summary statistics will generally be reported based upon observed data. Should a determination of treatment period (on treatment or pre-treatment) be required for adverse events or concomitant medication but the corresponding date is missing or partial, the event/medication will be considered on treatment unless the portions of the date that are available indicate this is not possible.

If a subject fails to complete their eDiary for a week or more, the WI-NRS endpoints, including the primary endpoint, may be missing. In this case, the WI-NRS change from baseline value will be imputed. The approach uses the subject's last week with data. From that point forward their trajectory will be imputed based upon the trajectory of their treatment group.

The imputation approach first determines the average change between analysis weeks (see [Table 4](#)) for each treatment group. The change between analysis weeks is the difference between results at adjacent analysis Weeks (e.g. results at Week 10 – results at Week 8). Any missing change from baseline results will be imputed by combining the last known value and the treatment group mean weekly differences from that point forward. CCI

This imputation algorithm is only used if the intercurrent events (see [Section 2.6](#)) did not occur.

For the responder endpoints, the same imputation will be performed and the responder status determined based upon the change from baseline.

Missing data imputation will only be used for the WI-NRS endpoints.

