2.8 Sensitivity Analyses, Subgroups and Covariates

Descriptive statistics for the WI-NRS responder rate at Week 10 will be provided for the subgroups indicated below. Forest plots of the difference and confidence interval for this difference will also be created. The subgroups include,

- Sex
- Age Group
 - (≤ 64 years, > 64 years)
 - (< 50 years, ≥ 50 years).
- Race - all race groups with less than 30 subjects will be combined with 'Other'

- Baseline WI-NRS (< 8.5, >= 8.5)
- Duration of chronic pruritus (< 1 yr, 1-5yrs,>5 yrs)

Additionally, the WI-NRS responder rates at Week 10 will be summarized for subject with and without the following post baseline events. These are post-baseline factors and may be correlated with treatment outcomes.

- Study Disposition
 - Completed study
 - Did not complete the study
- Ever require / did not require rescue therapy for treatment of worsening pruritus
- Treatment completion (completed treatment, did not complete treatment).

To investigate the impact of missing data, missing WI-NRS data will be derived using the method of Markov Chain Monte Carlo (MCMC) multiple imputation. Imputation will be conducted within each treatment group independently, so the pattern of missing observations in one treatment group cannot influence missing value estimations in another. The MCMC imputation will use the observed results at each timepoint. For each imputation process, 1000 imputations will be performed. To mimic the original missing data algorithm, the continuous values will be imputed and the responder status will be determined. The intercurrent events rules (see [Section 2.6](#)) will continue to be used. A CMH test, identical to the test used for the primary endpoint, will be used based upon the imputed responder status.

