3.4 Analysis of Efficacy Endpoints

3.4.1 Calculation Examples for Daily Measures

Below are examples of how the eDiary WI-NRS weekly results will be calculated based upon windows outlined in [Table 4](#) and rules outlined in [Section 2.4](#).

1. Example 1 (complete data)
 - a. The subject has results for all seven days leading up to the visit (e.g. $x_8, x_9, x_{10}, x_{11}, x_{12}, x_{13}, x_{14}$).
 - b. The average for Week 2 is $(x_8 + x_9 + x_{10} + x_{11} + x_{12} + x_{13} + x_{14})/7$.
2. Example 2 (incomplete data, completed in the extended range)
 - a. The subject has results for less than seven days in the original range (e.g. $x_{22}, x_{24}, x_{25}, x_{27}, x_{28}$) but have enough in the extended range to reach seven results overall (e.g. x_{29}, x_{31}). In this example the subject is missing diary data on days 23, 26, and 30.
 - b. The average for Week 4 is $(x_{22} + x_{24} + x_{25} + x_{27} + x_{28} + x_{29} + x_{31})/7$.
3. Example 3 (incomplete data)

- a. The subject has results for less than seven days in the original range (e.g. x_{39} , x_{40} , x_{42}) and does not have enough in the extended range to reach seven results overall (e.g. x_{44} , x_{46}). In this example the subject is missing diary data on days 36, 37, 38, 41, 43 and 45.
 - The average for Week 6 is $(x_{39}+x_{40}+x_{42}+x_{44}+x_{46})/5$.
4. Example 4 (no data)
 - a. The subject does not complete the diary from day 60 onwards.
 - b. The average for Week 10 is missing and the missing data rules ([Section 2.7](#)) are used.

3.4.2 *WI-NRS*

The WI-NRS endpoints (result, change from baseline, 3-point and 4-point responders) will be summarized at the primary time point (Week 10) as well as at Weeks 2, 4, 6, 8 and Follow-up. The summary measures will include 95% Wald confidence intervals for the treatment difference and a p-value for the treatment difference (for the change from baseline and responder rate measures). The baseline WI-NRS will also be summarized, but no confidence interval will be produced. A graph of the mean WI-NRS results and mean change from baseline results and the 4-point responder rate (baseline included with a rate of zero) by timepoint and treatment will be produced.

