The WI-NRS scores for days 1 to 14 will be plotted by averaging the available data across subjects within treatment group and study day. These results will be summarized in a table along with change from baseline, where baseline is defined in the identical manner used for the weekly measures. Daily WI-NRS results will be summarized in a table based upon availability of the data regardless of any intercurrent events.

The test used for the 3 and 4-point responder rates at Weeks 2, 4, 6, 8 and 10 is a CMH test controlling for the ‘as randomized’ stratification factors. The ‘as randomized’ stratification factors are based upon the stratification cell that the subject was randomized to. The differences between treatment groups for the change from baseline measure will be tested using an ANOVA model controlling for the stratification factors. A main effects model with an interaction term (treatment by stratification factors) and a Type II hypothesis will be used. The estimated treatment effect from this test will be a weighted average based upon the equation provided in [Section 2.5](#).

The WI-NRS 4-point responder rates at Week 10 will be summarized within the subgroups and separately by the post baseline factors outlined in [Section 2.8](#). Forest plots based upon the same groups will also be produced.

A missing data sensitivity analysis will be conducted using the multiple imputation method outlined in [Section 2.8](#). This analysis will include summary statistics by time points for the 4-point WI-NRS responder rate and the continuous WI-NRS measures as well as testing for the 4-point WI-NRS responder endpoint at Week 10. The following steps will be followed:

1. Using the daily eDiary data, the windows in Table 4 and the intercurrent rules outlined in Section 2.6 calculate the weekly WI-NRS values. Within this will be unknown values (i.e. no data within the Table 4 windows)
2. The missing WI-NRS values will be filled in using the MCMC method to generate at least 1000 datasets. [REDACTED] CCI [REDACTED]
[REDACTED]
[REDACTED]
[REDACTED]
3. From each dataset the responder status will be determined.
4. The resulting point estimates (Mantel Haenszel treatment effect and standard error) and the responder rate p-value from the data will be calculated using the SAS software procedure Freq.
5. These results will be combined with the SAS software procedure mianalyze.

3.4.3 *WI-VAS*

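### The primary Week 10 responder test treats a single deterministic imputation as observed data; the within-arm multiple imputation already planned as a sensitivity analysis should be primary

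*SAP*

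**What the plan says.** The primary endpoint is the WI-NRS 4-point responder rate at Week 10, tested by a stratified CMH test (SAP 2.5.1; Protocol 8.8.2).

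- **Missing values.** In SAP 2.7 a missing change is "imputed by combining the last known value and the treatment group mean weekly differences from that point forward". Protocol 8.2 says the same: "From that point forward their trajectory will be imputed based upon the trajectory of their treatment group". Its worked formula adds the arm's average increment to the subject's own last change and has no random term. Responder status is read from the filled value. Part of SAP 2.7 is redacted, so this point covers the visible text.
- **Who is imputed.** SAP Table 4 builds Week 10 from Days 64-70, extended back to Day 60. One entry in Days 60-70 is therefore enough to avoid imputation. The SAP 3.4.1 example of a missing Week 10 is "The subject does not complete the diary from day 60 onwards". After withdrawal for lack of efficacy or use of rescue, SAP 2.6 says the missing-data rules "will not be used for the results following an intercurrent event". Those scores are instead "set to the larger of baseline and the last WI-NRS value prior to the event", which makes the subject a non-responder.
- **Sensitivity analysis.** SAP 2.8 adds that "missing WI-NRS data will be derived using the method of Markov Chain Monte Carlo (MCMC) multiple imputation", within arm. SAP 3.4.2 pools the Mantel-Haenszel effect and its standard error with PROC MIANALYZE.
- **Decision.** SAP 1.6 tests at one-sided 5% and adds a second tier, beginning "If the one-sided p-value is additionally less than 2.5" (percent), which it treats as the usual evidence standard for efficacy.

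**The concern.** A mean-based fill can be adequate for estimating a mean. It is less suitable for a proportion beyond a threshold, for two reasons.

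First, the CMH variance takes each filled status as a real observation. All imputed subjects in an arm share the same estimated increments, so their statuses move together, and the test does not count this.

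Second, the filled values may have the wrong spread around -4, which makes the imputed responder share wrong. If the arms lose different amounts of data, these errors do not cancel.

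Both thresholds in SAP 1.6 rest on this one p-value. The multiple imputation might reveal a divergence, but no visible rule says which result would then prevail.

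**Working it through.** **1. The plan's own figure.** SAP 1.6 claims at least 90% power with 100 per arm at one-sided 5%. The planning rates are redacted, so the claim can be neither reproduced nor refuted. Solving n = [1.645·√(2p̄q̄) + 1.282·√(p1q1 + p2q2)]² / (p2 - p1)² for 25% versus 44.6% gives [(1.108 + 0.845) / 0.196]² ≈ 99 per arm. Other pairs giving 90% are 20% versus 38.7% and 30% versus 50.1%.

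**2. The mechanism.** For a subject last seen at week k, imputed Δ10 = own Δk + (arm mean at Week 10 - arm mean at week k). Take normal changes and dropout unrelated to outcome:

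- true responder share = Φ((-4 - μ10)/σ10)
- share among the imputed = Φ((-4 - μ10)/σk)

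Assume μ10 = -2.5 and σ10 = 2.5:

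- Truth: Φ(-0.6) = 27.4%.
- Constant SD (σk = 2.5): 27.4%, so no bias.
- Last seen with SD 1.5: Φ(-1.0) = 15.9%.
- No post-baseline week: Table 4 includes Baseline as an analysis week, so the fill is the arm mean, identical for everyone. The share is 0% when that mean is short of -4 and 100% when it is beyond.

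Hand check of the extreme case, where every missing subject lacks a post-baseline week and 25% (placebo) versus 10% (serlopitant) are missing: 0.75 × 27.4% = 20.6% and 0.90 × 27.4% = 24.7%. That is a spurious 4.1-point advantage for serlopitant. Simulation gave 20.5% and 24.7%.

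**3. Simulated one-sided error at 5%, no true effect.** All inputs below are assumed except 100 per arm, four strata and the cut.

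Model A: Week 10 SD 2.8, either constant or rising 60/75/87/95/100% over Weeks 2-10; correlation 0.8 per step; mean reaching 40/65/80/92/100% of its Week 10 value; null responder rates 20-36%. Dropout is monotone and completely random. Last observed visit none/2/4/6/8: early 30/25/20/15/10%, late 5/20/25/25/25%. There were 20,000 trials per setting; complete data gave 4.3-5.7%.

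| Missing, placebo/serlopitant | Late dropout | Early dropout |
|---|---|---|
| 15%/10% | 5.3-6.5% | 5.9-7.1% |
| 20%/10% | 5.7-7.1% | 6.6-8.9% |
| 30%/10% | 6.3-8.9% | 8.5-12.9% |
| 10%/20% | 4.7-5.7% | 3.7-4.4% |
| 10%/30% | 3.7-5.5% | 2.4-3.7% |
| 15%/15%, mean on -4 | 6.4-7.0% | 12.7-13.1% |

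Equal 5-15% missing gave 4.8-6.2% over both timings (2.4-3.3% at the 2.5% threshold). A repeat run gave 9.1-13.0% for 30%/10% early and 2.6-3.8% reversed. With constant SD and nobody lacking a post-baseline week, bias was about zero and error 4.4-6.5%.

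Model B: baseline uniform on 7-10, SD rising from 1.5 to 2.5, correlation 0.85 per step, dropout at random times, 8,000 trials; complete data 4.6-5.0%.

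- Mean -2.5: 15%/15% gives 5.3%, 25%/10% gives 8.5%, 10%/25% gives 3.5%.
- Mean -5 reverses the direction: 25%/10% gives 3.9%, 10%/25% gives 8.1%.
- Mean -4 with equal 15% missing gives 9.7%.
- The extreme case of step 2 gives 17.1%, and 1.0% reversed.

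**4. Multiple imputation.** Within-arm normal-model imputation (20-25 imputations, a stand-in for MCMC) with pooled Mantel-Haenszel differences. Without intercurrent events the error was 3.4-5.7% (A) and 3.6-4.7% (B), with bias at most 0.2 points in A. With assumed intercurrent events kept out of the imputation model it was 3.1-5.3% (A) and 3.5-4.8% (B). With the SAP 2.6 values left in, it was 2.2-7.7% (A). In B it was 3.3-4.7% when events tracked poor response, and 2.7-10.0% when 15-25% had events and dropouts were event-free.

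**5. Power, 24% versus 44% (A), multiple versus single imputation.** 10% missing: 89.6-90.5% versus 90.4-91.4%. 15%: 88.6-89.7% versus 88.4-91.6%. 20%: 87.0-89.2% versus 88.9-91.2%.

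**The case against.** **The rule keeps each subject's own last value.** Imputed values therefore carry the spread of the last observed week. This stands: with constant SD and at least one post-baseline week, step 2 shows no bias, and only a small understatement of variance remains.

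**The early-dropout pattern fits the protocol poorly.** Subjects who stop drug enter a 5-week follow-up with the daily diary running (Protocol 3.1, 5.6, Appendix A), and entry requires at least 80% diary completion. Having no post-baseline week needs almost immediate withdrawal or abandonment of the diary. This stands, so the early figures are a stress case. It does not remove imputation. With a last dose on Day 10, Follow-up falls on Days 45-52 (10 + 35 to 10 + 42) and the diary is collected before Day 60. That subject is imputed, but from a later week.

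**This is Phase 2 and multiple imputation is already planned.** True, and it limits the severity. It does not settle which result decides.

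A reader might infer more in three places.

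- *That the primary error is inflated in general.* The documents give no missing-diary rate, timing or SD to support that, and balanced, low missingness stays near nominal.
- *That a mean near -4 shifts the error either way.* With equal missingness it only inflates it. Both directions arise only when missingness is unequal.
- *That the planned multiple imputation is itself biased.* In SAP 3.4.2, step 1 has "the intercurrent rules outlined in Section 2.6 calculate the weekly WI-NRS values" before imputing, but SAP 2.8 says the imputation draws on observed results, and step 2 is partly redacted. The simulation also overwrote all later scores, whereas SAP 2.6 limits rescue overwriting to four weeks after rescue ends. The text is unclear, and bias is not established.

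**Conclusion.** The point holds within limits. The primary test ignores imputation variance in every case. Its imputed responder share is wrong only when some subjects have no post-baseline week or the SD of change grows over time.

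On assumed inputs the one-sided 5% error is about 5-6% with low, balanced missingness and a mean well short of -4. It is about 5-8% at 15%/10% to 20%/10% missing, with 8.9% the highest value found. In the stress case of 30%/10% with early dropout it is about 8.5-13%, and about 2.4-3.8% when reversed. The direction depends on which arm loses more data and on which side of -4 the mean lies.

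It is a cheap improvement: nobody can know beforehand that missingness will be benign, and the better method is already specified. That method relies on data missing at random and a reasonable imputation model.

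**What to change.** Before unblinding:

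1. Make the within-arm MCMC multiple imputation of SAP 2.8 and 3.4.2 the primary missing-data method for the Week 10 responder test. Take the one-sided p-value from the Mantel-Haenszel difference and standard error pooled by PROC MIANALYZE. Fix the seed and the number of imputations (SAP 2.8 says 1000, SAP 3.4.2 at least 1000).
2. Amend SAP 2.5.1 and 2.7 and Protocol 8.2 and 8.8.2 to match, because the pooled test replaces the single CMH p-value.
3. Reconcile SAP 2.8 with step 1 of SAP 3.4.2. State that values set under SAP 2.6 are treated as missing when the imputation model is fitted, and that the unchanged SAP 2.6 non-responder rule is applied afterwards. This is a clarification, unnecessary if the redacted text already says so.
4. Keep the arm-mean single imputation as a sensitivity analysis, and report the number of imputed Week 10 values by arm.

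Cost: document wording, since the code is already planned, and about 0-3 points of power at 10-20% missing (24% versus 44%). Power may fall slightly below 90% from 15% missing. At 36% versus 53% with 15% missing the gap was 4-10 points, but part of the single-imputation power there came from an overstated difference (+0.4 to +3.3 points).

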2.8 Sensitivity Analyses, Subgroups and Covariates

Descriptive statistics for the WI-NRS responder rate at Week 10 will be provided for the subgroups indicated below. Forest plots of the difference and confidence interval for this difference will also be created. The subgroups include,

- Sex
- Age Group
 - (≤ 64 years, > 64 years)
 - (< 50 years, ≥ 50 years).
- Race - all race groups with less than 30 subjects will be combined with 'Other'

- Baseline WI-NRS (< 8.5, >= 8.5)
- Duration of chronic pruritus (< 1 yr, 1-5yrs,>5 yrs)

Additionally, the WI-NRS responder rates at Week 10 will be summarized for subject with and without the following post baseline events. These are post-baseline factors and may be correlated with treatment outcomes.

- Study Disposition
 - Completed study
 - Did not complete the study
- Ever require / did not require rescue therapy for treatment of worsening pruritus
- Treatment completion (completed treatment, did not complete treatment).

To investigate the impact of missing data, missing WI-NRS data will be derived using the method of Markov Chain Monte Carlo (MCMC) multiple imputation. Imputation will be conducted within each treatment group independently, so the pattern of missing observations in one treatment group cannot influence missing value estimations in another. The MCMC imputation will use the observed results at each timepoint. For each imputation process, 1000 imputations will be performed. To mimic the original missing data algorithm, the continuous values will be imputed and the responder status will be determined. The intercurrent events rules (see [Section 2.6](#)) will continue to be used. A CMH test, identical to the test used for the primary endpoint, will be used based upon the imputed responder status.

